7.3. Study Measurements and Visit Schedule

The schedule of assessments for this study is presented in Table 1.

Table 1: Study Measurements and Visit Schedule

Assessments	Screening ¹	Baseline ¹ Pre-Dose	Day 1 ¹ Post-Dose	Day 3 ²	Day 7 (+ 2 days)	Day 14 ² (+3 days)	Early Withdrawal ³
Informed Consent/Assent	X						
Inclusion/Exclusion Criteria	X						
Pregnancy Test (Urine) ⁴	X				X		X
Medical History	X						
Body Temperature ⁵	X	X	X	X	X	X	X
Physical Exam		X					
Influenza Related Complications (IRC) ⁶		X		X	X	X	X
Vital Signs ⁷		X		X	X	X	X
Concomitant Medications Review ⁸	X	X	X	X	X	X	X
Clinical Chemistries and Hematology ⁹		X			X	X ¹⁷	X ¹⁷
Urinalysis ⁹		X			X	X ¹⁷	X ¹⁷
Assessment of influenza symptoms/ activities of daily living/ eating habits 10		X	X	X	X	X	X
Subject Diary Completion/ Review ¹¹		X	X	X	X	X	X
Nasal swabs for Virology Analysis ¹²		X		X	X	X	X
Study Drug Administration ¹³		X					
Serum sample for influenza antibody analysis ¹⁴		X			X		
Pharmacokinetic (PK) Sampling ¹⁵			X				
Adverse Events			X	X	X	X ¹⁶	X ¹⁶

¹ It is expected that the date of Screening, Baseline, and Day 1 (date of study drug administration) will be the same.

² The Day 3 visit may be performed as a clinic visit or home visit (conducted by a qualified study nurse). The Day 14 visit may be performed as a home visit, clinic visit, or phone call. In the event the Day 14 assessment is a phone call the parent/ caregiver will be requested to mail the completed diary card back to the site.

³ An Early Withdrawal assessment should be conducted for subjects who withdraw before Day 7. For subjects who withdraw between Day 7 and Day 14 a telephone assessment should be completed, where possible.

⁴ Urine pregnancy test will be performed for any female post-menarche.

BioCryst Pharmaceuticals, Inc. CONFIDENTIAL

BCX1812-305

- 5 The screening temperature may be performed per the site's standard method, which will be recorded. For subsequent visits, the parent/guardian will record oral or axillary temperature with the electronic thermometer provided by BioCryst, Thereafter, the parent/caregiver will record temperature in the Subject Diary approximately every 12 hours until temperature is normal for 48 hours without antipyretic.
- 6 If an IRC is suspected, then a targeted physical examination and if needed, diagnostic testing will be conducted to record the actual presence/absence of the IRC.

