- 7 Vital sign measures will include blood pressure (in children <2 only if clinically indicated), pulse rate, and respiration rate. Vital signs will be recorded at Baseline, and vital signs will be taken once on remaining study visit days.
- 8 Antipyretic medications will be recorded in the Subject Diary by the parent/caregiver daily from Day 1 through Day 14.
- 9 Clinical laboratory assessments performed at Baseline are for the purpose of establishing a baseline. Subjects may be enrolled and begin treatment with study drug prior to receiving results.
- 10 The severity of age appropriate influenza signs and symptoms will be recorded by the parent/caregiver in the Subject Diary twice daily, until all symptoms are resolved (Grade 0). Assessments of activities of daily living and eating habits will be recorded once daily until all symptoms are resolved.
- 11 On Day 1, the parents/caregivers of subjects and/or adolescent subjects are to be provided training by the study staff on completing the Subject Diary. Instructions will be reviewed with the adolescent subject or parent/caregiver at each study visit.
- 12 Swabs for virology analysis will be collected on Day 14 where possible.
- 13 Only for those subjects randomized to peramivir. The parents/caregivers of subjects randomized to the oral oseltamivir arm of the study, will record the date and time of each drug administration, from Day 1 until Day 5 (or last scheduled dose). The first dosing will be administered at the site and documented by the study staff following completion of required predose activities.
- 14 A single serum specimen will be collected, where possible, pre-dose on Day 1 and on Day 7 for analysis of influenza antibody titers. Subjects whose weight is < 10kg do not require a serum antibody sample.
- 15 Only for those subjects randomized to peramivir. A PK sample will be drawn immediately following the end of study drug infusion/administration, between 30 minutes to 1 hour post-infusion, between 1 and 3 hours post-infusion, and between 3 and 6 hours post-infusion. Note: Subjects ≥ 5 kg will have four 1.0 mL blood draws at the above stated sampling times. Subjects < 5 kg will have two 1.0 mL blood samples; one time immediately following completion of the infusion and one time between 1-3 hours post-infusion.

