8. SELECTION AND WITHDRAWAL OF SUBJECTS

8.1. Subject Inclusion Criteria

- 1. Male and non-pregnant female subjects age birth to 17 years of age.
- 2. Clinical signs and symptoms consistent with acute influenza infection consisting of an oral temperature ≥ 100°F (37.8°C) or rectal temperature ≥ 101.3°F (≥ 38.5°C) with at least one respiratory symptom (cough or rhinitis) OR a positive influenza rapid antigen test. Fever will either be documented at the time of screening or must be reported by the parent or care-giver if treatment with an antipyretic was given within 6 hours of the screening assessment. Note: enrollment at each site by clinical symptoms alone will be approved by the Sponsor at the beginning of each influenza season once influenza has been confirmed in the local community. The Sponsor may withdraw approval for symptomatic screening in any season based upon trends in influenza surveillance data. Prior to sponsor approval or after approval is withdrawn, criteria 2 must be met by a positive influenza RAT test. During the period of approval, clinical symptoms alone will be adequate to meet criteria 2.
- 3. Onset of symptoms no more than 72 hours before presentation for screening for subjects < 2 years old .
- 4. Written informed consent by parents/guardians and assent by subjects ≥ 7 years of age^{1,2}
- 5. Females who have started their menses must either be:
 - Sexually abstinent
 - Using a highly effective form of birth control such as hormone contraception (oral, patch, injection, implant or vaginal ring) or 2 barrier methods (condom with spermicide and diaphragm)

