9.8.4. Antipyretics and Analgesics

Resolution of fever is a major component of some of the clinical effectiveness endpoints for this study. Accordingly, use of any antipyretics or analgesics with antipyretic properties must be carefully controlled and documented. Antipyretics and analgesics may be administered while the subject is enrolled in this study. The names and dosages of these medications will be recorded in the Subject Diary. To avoid the confounding effects of antipyretic medications, temperature measurements, including those recorded by study staff while in the emergency department or clinic and those recorded by the subjects during the follow-up period, will be taken, whenever possible, at least 4 hours after administration of the antipyretic medication or immediately prior to administration. Following discharge from the hospital, the names and dosages of all other medications will be recorded in the Subject Diary by the parent/ care-giver.

Temperature measurements that are recorded for the purpose of analyzing effectiveness in this study < 4 hours after administration of the antipyretic medication, regardless of the dose, will not be counted in the effectiveness analyses.

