# Resolution of Fever

A subject has Resolution of Fever if he/she has a temperature < 99.4°F oral or < 98.4°F axillary and no antipyretic medications have been taken for at least 12 hours. Resolution of Fever is based on information obtained from the individual subject diaries.

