# **6.2.2.** Effectiveness Analyses

A subject's oral temperature will be summarized by age group and overall by study visit and treatment group. A subject has Resolution of Fever if he/she has an oral temperature <99.4°F oral or <98.4°F axillary and no antipyretic medications have been taken for at least 12 hours. The time to resolution of fever will be estimated for each age group and overall by treatment group using the method of Kaplan-Meier using temperature and symptom relief medication information obtained from the subject diary data. Subjects who do not have resolution of fever will be censored at the time of their last non-missing post-baseline temperature assessment.

Alleviation of symptoms will be determined by assessment of symptoms as reported on each Subject Diary. The time to alleviation of symptoms will be estimated overall and for individual symptoms for each age group by treatment group using the method of Kaplan-Meier. Subjects who do not experience alleviation of symptoms will be censored at the date of their last non-missing post-baseline assessment.

Change from baseline in  $TCID_{50}/mL$  through Day 3, Day 7 and Day 14 respectively will be presented by age group and overall by treatment group for subjects with positive viral titers at baseline ( $log_{10} \ TCID_{50}/mL > 0.5$ ). A box plot and a histogram of the  $TCID_{50}/mL$  values will be presented by visit, age group, and treatment group. In addition, the median change from baseline in  $TCID_{50}/mL$  will be presented by visit, age group, and treatment group.

The number and percent of subjects with positive viral titers at baseline ( $log_{10} TCID_{50}/mL > 0.5$ ) that are shedding virus at each visit will be presented by age group and overall by treatment group.

The RT-PCR results at each visit will be presented by age group and overall by treatment group for subjects with positive RT-PCR results at baseline.

Change from baseline to last positive value of influenza virus susceptibility to neuraminidase inhibitors will be assessed using virology laboratory tests. Virology laboratory tests will include phenotypic characterizations of influenza virus recovered (hemaglutinin and neuraminidase) and viral susceptibility to zanamivir, oseltamivir, and peramivir, as well as genotyping of virus isolates. These analyses will be presented overall and by age group, treatment group and viral subtype.

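### The 12-hour antipyretic-free check for fever resolution reads the Subject Diary only, so an antipyretic taken before study drug is not reliably counted and an early reading can be scored as resolution against the SAP's own definition

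*SAP*

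**What the plan says.** SAP 4.3.8, under Resolution of Fever, requires a temperature below the oral or axillary threshold and that "no antipyretic medications have been taken for at least 12 hours". The same entry names the source: "Resolution of Fever is based on information obtained from the individual subject diaries". SAP 6.2.2 repeats the restriction for the Kaplan-Meier analysis, "using temperature and symptom relief medication information obtained from the subject diary data". Protocol 13.8.2 gives the same 12-hour condition but names no data source, so the restriction to the diary is the SAP's. Time to event is counted from the start of study treatment.

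On antipyretics before dosing, Protocol 8.1 accepts fever that "must be reported by the parent or care-giver if treatment with an antipyretic was given within 6 hours of the screening assessment". Table 1, footnote 1, adds: "It is expected that the date of Screening, Baseline, and Day 1 (date of study drug administration) will be the same". On diary coverage, Table 1, footnote 8, says: "Antipyretic medications will be recorded in the Subject Diary by the parent/caregiver daily from Day 1 through Day 14". Table 1 marks the diary at Baseline pre-dose, but Protocol 10.2.2.2 lists caregiver training among the post-dose activities, and its list of items to record has no separate entry for antipyretics.

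Medications are also reviewed at Screening and Baseline (Table 1; Protocol 9.8). The SAP classes anything taken before study drug as a previous medication, and SAP 6.3.2 presents previous medications in a listing. Nothing in the SAP links that record to the fever endpoint.

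**The concern.** A 12-hour look-back needs 12 hours of antipyretic history before the reading. For a reading in the first hours after dosing, some of that history precedes study drug. A programmer following SAP 4.3.8 and 6.2.2 would search the diary alone, find no antipyretic if the pre-dose one was never entered, and accept the reading.

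Time to resolution of fever is a named secondary endpoint, and Protocol 9.8.4 stresses that antipyretic use must be controlled and documented because of it. The study tests no hypothesis, so the estimated times are themselves the result. Missing a dose can only let a reading qualify that should not, so the error runs in one direction, toward early resolution.

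**Working it through.** The plan states no figure on this point, so there is nothing to reproduce. The check is timing arithmetic.

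**Inputs.** Antipyretic-free requirement: 12 h (SAP 4.3.8). Readings not counted after an antipyretic: those taken less than 4 h later (Protocol 9.8.4 and 10.3.1; not repeated in the SAP). Reading schedule: about every 12 h (Protocol 10.1). Antipyretic contemplated at eligibility: up to 6 h before screening (Protocol 8.1). Interval from screening to dosing: same day expected, hours not given.

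**Formula.** Let the antipyretic be taken a hours before study drug and the reading t hours after it. The true antipyretic-free time is a + t. The 12-hour condition fails when a + t < 12, that is, t < 12 - a. The 4-hour rule removes readings with t < 4 - a.

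| a (h) | Fails 12-hour condition | Removed by 4-hour rule | Exposed window left |
|---|---|---|---|
| 0 | t < 12 | t < 4 | 8 h |
| 2 | t < 10 | t < 2 | 8 h |
| 4 | t < 8 | none | 8 h |
| 6 | t < 6 | none | 6 h |
| 8 | t < 4 | none | 4 h |
| 10 | t < 2 | none | 2 h |
| 12 | none | none | 0 h |

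The third column applies only if the analysis knows of the dose. If it reads the diary alone and the dose is not there, the 4-hour rule misses it too, and the whole second column is exposed.

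**Two examples with invented clock times.**

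- Same day: antipyretic 09:00, study drug 10:30, normal reading 18:00. Then a = 1.5, t = 7.5 and a + t = 9 h, which is under 12. If the 09:00 dose is not in the diary, resolution is scored at 7.5 h. The 4-hour rule would not remove this reading, because 9 > 4.
- Across midnight: antipyretic 22:00, study drug 01:00. Then a = 3 and the window is 12 - 3 = 9 h. This dose falls on the day before Day 1 and so before footnote 8's recording period starts.

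**Effect on one child.** With readings about 12 h apart, rejecting an early reading moves the event to the next qualifying one, about 12 h later or more. Only a child with a below-threshold reading inside the window is affected.

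**Effect on the estimate.** This would need the share of children pre-medicated, the times of those doses and the share not entered in the diary. The documents give none of these.

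**The case against.** The strongest reply is that the diary may hold the dose. A reader might infer that pre-dose antipyretics are invisible to the analysis. The documents do not support that: footnote 8 starts recording on Day 1, Table 1 marks the diary before dosing, and Protocol 9.8 has caregivers record the date, time and dose of antipyretics. A same-day dose before study drug may well be entered. What remains is that nothing requires it, that training is listed after dosing, and that a dose on the previous calendar day is outside the stated period. Previous-evening doses often have a large a, and so a short window.

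A reader might also infer that in-hospital antipyretics are missed, from "Following discharge from the hospital, the names and dosages of all other medications will be recorded in the Subject Diary by the parent/ care-giver". That sentence concerns other medications. Earlier in the same section, antipyretics and analgesics go into the diary with no discharge condition, so the inference fails.

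Nor do the documents show that an accepted reading is drug-suppressed. The protocol uses 4 hours to avoid antipyretic confounding, so a reading 9 hours after a dose fails the 12-hour definition without being shown to be false.

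Finally, a reader might put a number on the bias from the 20.4 h median time to normal temperature in the earlier pediatric study (Protocol 5.3.2.1). That needs an assumed share of affected children, and that study's endpoint used a threshold of 37.5°C with no antipyretic-free condition mentioned. It is not evidence of size here.

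**Conclusion.** The point stands in a limited form. Followed as written, the SAP can score as resolved a reading that fails its own 12-hour condition, because the check is confined to a source that need not contain pre-dose antipyretics. The exposed period is 12 - a hours after study drug. The full 12 hours is only the limiting case of an antipyretic given at dosing.

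The direction is toward early resolution; the size is unknown. The conclusion assumes that some children have an antipyretic within 12 hours before a post-dose reading, which the eligibility text makes likely, and that some of those doses are not in the diary, which the documents leave open.

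A reader might infer a distorted treatment comparison. The documents do not take it that far: the endpoint is secondary and descriptive, and the rule applies equally to both randomized arms. Nor were the cohorts under 7 years entirely uncontrolled, since part of their enrollment before amendment 3 was randomized. The main risk is to the absolute Kaplan-Meier times, which matter most for children under 7 enrolled after that amendment, who have no concurrent control.

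**What to change.** Amend SAP 4.3.8 and 6.2.2 as follows.

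1. Evaluate the 12-hour condition on the diary plus the Screening/Baseline previous and concomitant medication record, using clock times where available. Confirm that this record holds antipyretics, since Protocol 9.8 sends antipyretics to the diary and the other medications to the CRF.
2. Carry into the SAP the protocol's exclusion of readings taken less than 4 hours after an antipyretic, applied to the same combined record.
3. For a pre-dose antipyretic recorded without a clock time, state one primary convention and report a sensitivity analysis under the other. Two conventions bracket the result: treat the dose as taken at study dosing (a = 0, so no reading before 12 h qualifies), or as taken at least 12 h before (no restriction).
4. Report how many children had a recorded antipyretic in the 12 hours before study drug and how many event times change. This supplies the size that is now missing.

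A blanket rule rejecting every early reading unless the CRF confirms 12 drug-free hours is not advised, because it would turn missing times into later events.

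The cost is SAP wording and a merge of data that are mostly collected already. Some pre-dose times may be missing and, for children already enrolled, not recoverable. The median time to resolution may become slightly longer.

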#### Time to Event

Time to a given event is defined as the number of hours from initiation of earliest study treatment until the event occurs. The unit of measurement will vary based upon the endpoint and its respective schedule of assessment.

# Time to Alleviation of Symptoms

Time to Alleviation of Symptoms is the number of hours from initiation of study drug to start of the period in which a subject has Alleviation of Symptoms.

# Change from Baseline

Change from baseline for a given endpoint is defined as the Study Day X value minus the Baseline Value.

#### Adverse Event (AE)

According to the protocol, an AE is any untoward medical occurrence in a clinical study subject. No causal relationship with the study drug or with the clinical study itself is implied. An AE may be an unfavorable and unintended sign, symptom, syndrome, or illness that develops or worsens during the clinical study. Clinically relevant abnormal results of diagnostic procedures including abnormal laboratory findings (e.g., requiring unscheduled diagnostic procedures or treatment measures, or resulting in withdrawal from the study) are considered to be AEs.

AEs may be designated as "nonserious" or "serious" (see Protocol Section 11.1.1.1). Surgical procedures are not AEs but may constitute therapeutic measures for conditions that require surgery. The condition for which the surgery is required is an AE, if it occurs or is detected during the study period. Planned surgical measures permitted by the clinical study protocol and the conditions(s) leading to these measures are not AEs, if the condition(s) was (were) known before the start of study treatment. In the latter case the condition should be reported as medical history.

Assessment of age appropriate symptoms of influenza will be documented in a Subject Diary and analyzed as a measure of effectiveness of the study treatment. These symptoms will not be reported as AEs unless the symptom(s) worsen to the extent that the outcome fulfills the definition of an SAE, which then must be recorded as such (see Protocol Section 11.1.1.2). Likewise, a RAT for influenza is required at screening in order to determine eligibility for the study, and therefore a positive RAT is not considered an AE.

All adverse events will be recorded on the ADVERSE EVENTS CRF.

#### Treatment-emergent Adverse Event

Any event reported on the CRF that occurs on or after the initiation of study drug and not more than 14 days after the last dose of study medication is considered treatment-emergent. Additionally, it is assumed that an Adverse Event which was reported to have started on Day 1 without an associated onset time may have occurred after the initiation of study drug. Hence, Adverse Events occurring on Day 1 with no associated onset time are assumed to be treatment-emergent.

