The following procedures/assessments will be performed on Day 14 (+ 3 days). The Day 14 assessments will be performed as a clinic visit, home visit (conducted by a qualified study nurse) or, if either of these options are not possible, by phone call. If conducted by phone, the Day 14 assessments will be limited to interview assessment for the presence of possible influenza-related complications, concomitant medication use and AEs. The subject's parent/ caregiver will be asked to return the completed Subject Diary by mail.

- Body temperature (using the study electronic thermometer via the oral or axillary method).
- Assessment of presence of possible influenza-related complications.

- Vital sign measurements (blood pressure (in children < 2 only if clinically indicated), heart rate, respiration rate).
- Review of the Subject Diary for completeness.
- Determination (and recording in the Subject Diary) of the presence and severity of each of age appropriate symptoms of influenza. Question asked of subjects age 6 years and older, if possible.
- Determination (and recording in the Subject Diary) [with assistance from the subject (if possible)] of the subject's ability to perform usual daily activities.
- Determination (and recording in the Subject Diary) of the subject's appetite and eating patterns assessed as either normal or reduced/abnormal
- Bilateral adequate nasal swab specimen collection for viral culture, quantitative PCR assay and susceptibility to neuraminidase inhibitors.
- Review and recording of concomitant medications.
- Recording of any AEs.
- If previous lab results are abnormal and considered clinically significant by the Investigator or significantly changed from baseline, blood specimen collection for clinical chemistry or clinical hematology tests as specified in Sections 11.2.1 and 11.2.2 may be drawn.
- If previous lab results are abnormal and considered clinically significant by the Investigator or significantly changed from baseline, urine collection for urinalysis may be completed.

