#### 4.2. RANDOMIZATION AND MASKING

Approximately 140 subjects will be enrolled. Up to 10 subjects from birth to < 28 days will be enrolled to receive a single dose of IV peramivir. Up to 20 subjects from 28 days to < 2 years will either be randomized to 1 of 2 treatment arms at a ratio of 4:1 or will receive a single dose of IV peramivir. Up to 110 subjects from 28-days to < 18 years of age will be randomized to 1 of 2 treatment arms at a ratio of 4:1:

- Treatment Group 1: A single dose of IV peramivir
- Treatment Group 2: Oral oseltamivir given BID for 5 days

This is an open label study and as such, blinding is not applicable.

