# Study Day

Study Day is defined relative to Baseline (Day 1). Thus, the study day of an event is calculated as: Study Day = event date – date of Day 1 +1.

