# **Treatment-emergent Laboratory Abnormality**

A treatment-emergent laboratory abnormality is defined as an increase of at least one toxicity grade from the baseline assessment at any post baseline visit up to and including 14 days after the last dose date of study drug. If no assessment is available at baseline, the screening assessment will be used to assign the baseline toxicity grade. If the relevant baseline and screening assessments are

missing, then any graded abnormality (i.e., at least Grade 1) is considered to be treatmentemergent.

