#### 6.3. SAFETY

#### **6.3.1.** Adverse Events

Adverse events will be mapped to a Medical Dictionary for Regulatory Activities (MedDRA) version 18.0 preferred term and system organ classification. If a subject experiences multiple events that map to a single preferred term, the greatest severity grade and strongest investigator assessment of relation to study medication will be assigned to the preferred term for the appropriate summaries. Should an event have a missing severity or relationship, it will be classified as having the highest severity and/or strongest relationship to study medication. Summaries of treatment-emergent AEs will include any AEs reported beginning with the initiation of study drug on Day 1. The occurrence of treatment-emergent adverse events (TEAEs) will be summarized by treatment group using preferred terms, system organ classifications, and severity. Separate summaries of treatment-emergent serious adverse events, treatment-emergent adverse events related to study drug, and events leading to the discontinuation of study will be generated. All adverse events reported will be listed for individual subjects showing both verbatim and preferred terms. All adverse events that occurred prior to the initiation of study treatment or more than 14 days post-study drug discontinuation will be excluded from the tables but will be included in the listings.

Missing onset dates will be imputed as previously outlined in Section 4.3.5 as required to determine treatment-emergent events.

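### The treatment-emergent window is tied to the last dose, so onsets on Days 16–17 at a late final visit are tabulated for oseltamivir but only listed for peramivir

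*SAP*

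**What the plan says.** SAP 4.3.8 calls an adverse event recorded on the CRF treatment-emergent under this timing rule: it "occurs on or after the initiation of study drug and not more than 14 days after the last dose of study medication". Its definition of a treatment-emergent laboratory abnormality uses the same end point: a grade increase "at any post baseline visit up to and including 14 days after the last dose date of study drug". SAP 6.3.1 applies the limit to the tables: adverse events "more than 14 days post-study drug discontinuation will be excluded from the tables but will be included in the listings". SAP 6.3.3 repeats this for laboratory toxicities.

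The two regimens end on different days. SAP 4.2 gives "Treatment Group 1: A single dose of IV peramivir" for one arm and twice-daily oseltamivir for 5 days for the other. The visit calendar is common to both: Days 3, 7 and 14 counted from Day 1 (Protocol 7.3, Table 1). The final visit may take place up to 3 days late, and recording adverse events is one of its procedures (Protocol 10.2.2.5). Protocol 11.1.2, however, ends adverse event collection at Day 14.

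**The concern.** The primary objective is the safety of peramivir compared with oseltamivir, and the adverse event and laboratory tables are its main output. A counting rule that runs from the last dose gives the single-dose arm an earlier cut-off than the 5-day arm, while the children are observed over the same days. Wherever an event falls between the two cut-offs and is recorded, it enters the table for one drug and not the other. The test drug has the shorter window, so any resulting bias favours it. The rule also makes an oseltamivir child's window depend on when that child stopped taking the drug. The question is how much recorded data can fall between the two cut-offs.

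**Working it through.** The plan gives no figure of its own here; the check is day arithmetic.

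**Inputs**
- Study Day = event date − date of Day 1 + 1 (SAP 4.3.8). Calendar dates are assumed for the 14-day count.
- Peramivir last dose: Day 1 (SAP 4.2).
- Oseltamivir last dose: Day 5 (study drug footnote to the schedule, Protocol 7.3 and SAP 2.2). Day 6 is an assumption for a child who starts late on Day 1.
- End of adverse event collection: Day 14 (Protocol 11.1.2).
- Latest in-window final visit: 14 + 3 = Day 17 (Protocol 10.2.2.5). The SAP 2.2 schedule shows ±3 days, with the same late edge.
- Scheduled post-baseline laboratory tests: Day 7 (+2), so Days 7 to 9 (Protocol 10.2.2.4, 11.2.1 to 11.2.3). A Day 14 repeat is optional and follows only a clinically significant or significantly changed earlier result (Protocol 10.2.2.5).
- Planned peramivir subjects: about 117 of 140 (Protocol 13.4).

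**Step 1. Nominal window end = last dose day + 14**
- Peramivir: 1 + 14 = Day 15.
- Oseltamivir: 5 + 14 = Day 19 (6 + 14 = Day 20).
- Nominal gap: 4 to 5 days.

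**Step 2. Effective end = the earlier of the nominal end and the last day on which onsets are recorded**

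| Last recorded day | Peramivir | Oseltamivir | Gap |
|---|---|---|---|
| 14 | 14 | 14 | 0 |
| 15 | 15 | 15 | 0 |
| 16 | 15 | 16 | 1 day (1/15 = 6.7%) |
| 17 | 15 | 17 | 2 days (2/15 = 13.3%) |

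A Day 6 last dose changes nothing in this table, since Day 20 is also beyond Day 17.

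**Step 3. Laboratory tests.** Samples on Days 7 to 9, or on Day 14, are no later than Day 15 and count in both arms. SAP 6.3.3 limits the shift tables to baseline-to-Day 7. Only an optional repeat on Day 16 or 17 is treated differently: after Day 15, before Day 19.

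**Step 4. After Day 17.** A new onset on Day 18 or 19, recorded at a discretionary follow-up visit, is tabulated for oseltamivir (last dose Day 5) and only listed for peramivir. From Day 20 both are only listed.

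**Step 5. Early stopping of oseltamivir.** A last dose on Day 1, 2 or 3 closes the window on Day 15, 16 or 17. The gap at a Day 17 visit is then 0, 1 or 2 days, so the cut-off varies with adherence.

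**Step 6. Size.** One peramivir child whose only event is left out of the table changes that arm's rate by 1/117 = 0.9 percentage points.

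**Step 7. With a common end at Day 17.** Both effective ends are Day 17 for a Day 17 visit, and the gap is 0.

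**The case against.** The strongest reply is Protocol 11.1.2. If adverse events are collected only to Day 14, both cut-offs lie beyond the data and the gap is zero. Scheduled laboratory data stop at Days 7 to 9. A repeat on Day 16–17 changes a count only if it is the first to show a grade increase, and a telephone Day 14 assessment yields no sample. Discretionary visits exist to follow findings already open, so new onsets there should be rare. Influenza symptoms and complications, plausible late events, are not adverse events unless serious. Excluded events remain in the listings, and no hypothesis is tested (Protocol 13.3).

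Most of this stands and limits the point. It does not remove it, because the Day 14 limit is not carried through. The final visit may fall on Day 17 and includes recording adverse events, and nothing tells sites to leave out onsets on Days 15 to 17. The SAP definition covers whatever is on the CRF. SAP 6.3.1 also provides for events beyond the 14 days. Within the visit window that exclusion applies to peramivir, and otherwise only to an oseltamivir child who stopped on Day 1 or 2.

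A second defence is that a fixed interval after the last dose gives each drug the same post-exposure period. That rationale is reasonable, but the visit calendar does not deliver it: with a last dose on Day 5, a Day 17 final visit gives 17 − 5 = 12 days, not 14.

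**Conclusion.** The point holds as a low-impact inconsistency. The last-dose anchor gives cut-offs of Day 15 and about Day 19 on a shared calendar. The difference affects only new onsets or optional repeat laboratory results on Days 16–17 at a late final visit, or on Days 18–19 at discretionary follow-up. Within the visit window the gap is at most 2 days of counted time, and the direction favours peramivir. The 13.3% in the working is a ceiling on counted time for a child seen on Day 17, not an expected difference in event rates.

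A reader might infer that the primary adverse event and laboratory comparison as a whole rests on unequal observation windows. The documents do not support that: planned collection to Day 14 and the scheduled laboratory tests fall inside both windows. A reader might also size the effect on the smaller arm, 1/(140 − 117) = 1/23 = 4.3 points. That is the wrong arm. Within the visit window the oseltamivir count is already complete for a child who takes the drug through Day 3 or later, and the events left out are peramivir events at about 0.9 points each. Nor are they lost, since they stay in the listings.

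This rests on three assumptions: the 14 days are calendar dates, oseltamivir is taken to Day 5, and sites record onsets up to the actual final visit. If sites stop strictly at Day 14, the effect is nil. The documents do not give the number of late final visits or late onsets, so no expected count can be stated.

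**What to change.** Use one window anchored to the first dose for both arms: onset (or laboratory grade increase) from the first dose through the Day 14 visit including its 3-day allowance, at latest Day 17. Make the change in both SAP 4.3.8 definitions and in the exclusion sentences of 6.3.1 and 6.3.3. Reconcile it with Protocol 11.1.2, stating whether onsets between Day 14 and a later final visit are to be collected. Keep later events in the listings for both arms.

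The change is to wording and needs no new assessments. The peramivir rate may become very slightly less favourable. An oseltamivir onset on Day 18 or 19 found at discretionary follow-up would move from the tables to the listings, as it already does for peramivir.
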